#### 2. Linear Regression

For a given absolute change in PRO assessment scale summary score: the estimate of the numerical change in summary score that is associated with the transition between adjacent CCG categories will be determined using linear regression. Separate models will be fitted for improving and deteriorating scores based on the anchor. The outcome variable is the PRO assessment summary score, and the covariate is a binary anchor variable; coded as 'no change'=0 and 'small positive change'=1 for model on improvement (Other CCG categories are excluded from the linear regression model), and 'no change'=0 and 'small negative change'=1 for model on deterioration (Other CCG categories are excluded from the linear regression model). The resulting  $\beta$ 's (i.e. slope parameters) correspond to the MIDs for improvement and deterioration respectively. No other covariates will be included in these models.

PRO analysis will be performed for the Safety/ITT population.

#### 3.2.7.2.5.1 G-SET/HTI

G-SET/HTI is a single item, and will be used as an external anchor to determine the minimal important difference of EQ-5D-VAS, EORTC QLQ-C30, and QLQ-BIL21 scales. The G-SET/HTI is a patient-rated change in health between two time periods using a five-point ordinal scale (1=much better now than 8 weeks ago; 2=somewhat better now than 8 weeks ago; 3=about the same as 8 weeks ago; 4=somewhat worse now than 8 weeks ago). G-SET/HTI will be summarized at Cycle 3, Day 1, and Cycle 5, Day 1 by categorical and continuous descriptive statistics.

#### 3.2.7.2.5.2 EORTC QLQ-C30

EORTC QLQ-C30 was developed to assess the quality of life of cancer patients and is the most widely used cancer-specific HRQoL instrument. It contains 30 items and measures five functional scales (physical, role, cognitive, emotional, and social); three symptom scales (fatigue, pain, and nausea and vomiting); six single symptom items (dyspnea, sleep disturbance, appetite loss, constipation, diarrhea and financial impact) and a global health and quality-of-life scale. The global health and quality of life items uses a 7-point scale scoring from 1 (very poor) to 7 (excellent). The other items are scored on a 4-point scale from 1 (not at all) to 4 (very much). A high score for a functional scale represents a high/healthy level of functioning. A high score for the global health status represents a high QoL. However, a high score for a symptom scale/item represents a high level of symptomatology/problems. The scoring method is outlined in Table 6 and the following paragraphs.

#### STATISTICAL ANALYSIS PLAN BASILEA PHARMACEUTICA: DZB-CS-301

	0 4	-			
	Scale	Number of items	Item range	Version 3.0 Item numbers	Function scales
Global health Status /QoL	QL	2	6	29, 30	
Functional Scales					
Physical functioning	PF	5	3	1 to 5	F
Role functioning	RF	2	3	6,7	F
Emotional functioning	EF	4	3	21 to 24	F
Cognitive functioning	CF	2	3	20, 25	F
Social function	SF	2	3	26, 27	F
Symptom scales/items					
Fatigue	FA	3	3	10, 12, 18	
Nausea and vomiting	NV	2	3	14,15	
Pain	PA	2	3	9, 19	
Dyspnea	DY	1	3	8	
Insomnia	SL	1	3	11	
Appetite loss	AP	1	3	13	
Constipation	CO	1	3	16	
Diarrhea	DI	1	3	17	
Financial difficulties	FI	1	3	28	

### Table 6: Scoring the QLQ-C30 version 3.0

Raw score (RS) is calculated as the average of item score when at least half of the items are not missing. A linear transformation to 0-100 will then be applied to get the score (S) using the item range provided in Table 6.

For functional scales  $S = (1-(RS-1)/range) \times 100$ 

For symptom scales/items and global health status  $S = ((RS-1)/range) \times 100$ 

Each scale will be summarized at each visit as a continuous variable using descriptive statistics per substudy for the total scores, change from baseline and percent change from baseline for all visits where the EORTC QLQ-C30 is collected. In addition, at C5D1, the change from C3D1 at C5D1 and the percentage change at C5D1 from C3D1 will also be reported. For each of the functional scales, the minimally important change from baseline at C3D1 and change from C3D1 at C5D1 will be determined using the two methods detailed in Section 3.2.7.2.5.

#### 3.2.7.2.5.3 EORTC QLQ-BIL21

The EORTC QLQ-BIL21 comprises five multi-item measures of cholangiocarcinoma and gallbladder cancer-associated symptoms (eating symptoms, jaundice, tiredness, pain symptoms, anxiety), and three single items on treatment side effects, difficulties with drainage bags/tubes, and concerns regarding weight loss. The response is a four-point Likert scale.

	Number of items	Version 3.0 Item numbers	
Eating	4	31, 32, 33, 34	
Jaundice	3	35, 36, 37	
Tiredness	3	38, 39, 40	
Pain	4	41, 42, 43, 44	
Anxiety	4	45, 46, 47, 48	
Treatment Side Effects	1	49	
Drainage Bag/Tube Difficulties	1	50	
Weight Loss Concerns	1	51	

#### Table 7: Scoring the QLQ-BIL21

Raw score (RS) is calculated as the average of item score when at least half of the items are not missing. A linear transformation to 0-100 will then be applied to get the score (S) using the item range provided in Table 7.

For functional scales  $S = (1-(RS-1)/range) \times 100$ 

For symptom scales/items and global health status  $S = ((RS-1)/range) \times 100$ 

Each scale will be summarized at each visit as a continuous variable using descriptive statistics per substudy for the total scores, change from baseline and percent change from baseline for all visits where the EORTC QLQ-BIL21 is collected. In addition, at C5D1, the change from C3D1 at C5D1 and the percentage change at C5D1 from C3D1 will also be reported. For each of the functional scales, the minimally important change from baseline at C3D1 and change from C3D1 at C5D1 will be determined using the two methods detailed in Section 3.2.7.2.5.

3.2.7.2.5.4 EQ-5D (5L)

The EQ-5D (5L) is a standardized instrument for use as a measure of health outcome. The five health state dimensions in this instrument include the following: mobility, self-care, usual activities, pain/discomfort, and anxiety/depression. Each dimension is rated on a five-point scale from 1 (no problem) to 5 (extreme problem). The EQ-5D (5L) also includes a graded (0 to 100) VAS on which the patient rates his or her general state of health at the time of the assessment.

The 5 questions will be summarized descriptively as categorical variables for all visits where the EQ-5D (5L) is collected. The VAS will be summarized as a continuous variable using descriptive statistics for the total scores, change from baseline and percent change from baseline for all visits where the EQ-5D (5L) is collected. In addition, at C5D1, the change from C3D1 at C5D1 and the percentage change at C5D1 from C3D1 will also be reported. The minimally important change from baseline at C3D1 and change from C3D1 at C5D1 of the EQ-5D (5L) VAS will be determined using the two methods detailed in Section 3.2.7.2.5. Missing VAS scores will not be included in summary statistics and only patients with both an observation at the specified visit and at baseline will be included in change from baseline summaries.

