#### 6.10 Patient-reported outcomes

HRQOL and symptom response will be measured using the EORTC QLQ-C30 QLQ-BIL21, the EQ-5D, and the G-SET/HTI. Guidelines for completion of these instruments are provided in Appendix 7.

The EORTC QLQ-C30 measures five functional dimensions (physical, role, emotional, cognitive, and social), three symptom scales (fatigue, pain, and nausea and vomiting), six single symptom items (dyspnea, sleep disturbance, appetite loss, constipation, diarrhea, and financial impact), and global health and quality-of-life.

It will be administered in conjunction with a disease-specific quality of life questionnaire QLQ-BIL21, which is the only scale focusing specifically on the HRQoL of patients with cholangiocarcinoma. The EORTC QLQ-BIL21 comprises five multi-item measures of cholangiocarcinoma and gallbladder cancer-associated symptoms (eating symptoms, jaundice, tiredness, pain symptoms, anxiety), and three single items on treatment side effects, difficulties with drainage bags/tubes, and concerns regarding weight loss (Kaupp-Roberts 2016).

The EQ-5D is a standardized instrument measuring health outcomes, with five health state dimensions: mobility, self-care, usual activities, pain/discomfort, and anxiety/depression. The EQ-5D also includes a graded vertical visual analog scale (VAS) on which the patients rate their general state of health at the time of the assessment.

The G-SET/HTI is a single item, and will be used as an external anchor to determine the minimal important difference of the EQ-5D VAS, EORTC QLQ-C30, and QLQ-BIL21 scales. It will be administered twice during the study, consistent with the protocol by the EORTC Quality of Life Group (Musoro 2018) for evaluating the minimal important difference. The G-SET/HTI will be provided after 8 weeks (at Cycle 3 Day 1) and 16 weeks (at Cycle 5 Day 1). The G-SET/HTI is a patient-rated change in health between two time periods using a five-point ordinal scale (1=much better now than 8 weeks ago; 2=somewhat better now than 8 weeks ago; 5=much worse now than 8 weeks ago) (adapted from Ware 2002, Lloyd 2014).

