#### 1.2.2 Secondary objectives

#### Substudy 1 and Substudy 2

- To evaluate PFS by central radiology review and overall survival (OS)
- To evaluate duration of response (DoR) by central radiology review
- To evaluate the safety profile (toxicities) of derazantinib in this patient population
- To evaluate changes, and assess the minimally important difference, in HRQoL and symptom response from baseline using the EORTC QLQ-C30, QLQ-BIL21, G-SET / HTI, and the EQ-5D VAS

#### Substudy 2

• To evaluate the anti-cancer activity by ORR by central radiology review as per RECIST version 1.1 in patients with inoperable or advanced iCCA whose tumors harbor *FGFR2* mutations or amplifications, and who received at least one prior regimen of systemic therapy

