#### 3.2.7.2.5 PRO Assessments (Substudy 1 and Substudy 2)

For each assessment the minimally important difference (MID) in a score at C3D1 and C5D1 will be determined following the recent protocol by the EORTC Quality of Life Group (Musoro 2018). Patients with complete data will be categorized into five mutually exclusive clinical change groups (CCG) reflecting the five possible levels of change. For each pair of timepoints (Change in summary score from baseline at

C3D1 and Change in summary score from C3D1 at C5D1), a patient can thus belong to only one CCG category. Two methods for determining the MID will be explored:

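### SAP 3.2.7.2.5.3 limits QLQ-BIL21 MID estimation to functional scales, which the instrument as described does not have, in conflict with the SAP's own objective and general MID rule

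*SAP*

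**What the plan says.** The secondary objective in SAP 1.2.2 reads: "To evaluate changes, and assess the minimally important difference, in HRQoL and symptom response from baseline using the EORTC QLQ-C30, QLQ-BIL21", with the G-SET/HTI and EQ-5D VAS also listed. Protocol 2.2 states the same objective. Neither limits it to functioning, and both include symptom response.

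The parent section, SAP 3.2.7.2.5, sets a general rule: "For each assessment the minimally important difference (MID) in a score at C3D1 and C5D1 will be determined". It then gives two methods, mean change and linear regression. SAP 3.2.7.2.5.1 describes the G-SET/HTI as an "external anchor to determine the minimal important difference of EQ-5D-VAS, EORTC QLQ-C30, and QLQ-BIL21 scales". Protocol 6.10 gives the item the same purpose, to determine the "minimal important difference of the EQ-5D VAS, EORTC QLQ-C30, and QLQ-BIL21 scales".

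SAP 3.2.7.2.5.3 says the QLQ-BIL21 "comprises five multi-item measures of cholangiocarcinoma and gallbladder cancer-associated symptoms" and adds three single items, on treatment side effects, drainage bags or tubes, and weight-loss concerns. The text under Table 7 then gives one formula for functional scales and one for symptom scales and global health status. It provides descriptive summaries for every scale and closes with the MID sentence: "For each of the functional scales, the minimally important change from baseline at C3D1 and change from C3D1 at C5D1 will be determined".

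The QLQ-C30 section (3.2.7.2.5.2, under Table 6) has the same sentence, beginning: "For each of the functional scales, the minimally important change from baseline at C3D1". Table 6 marks five QLQ-C30 scales as functional.

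**The concern.** The sentence that picks the QLQ-BIL21 scores for MID estimation picks a class of scale that the instrument, on the SAP's own description, does not contain. A programmer who works from the instrument section would produce no QLQ-BIL21 MID. One who works from the parent section would produce some, but would have to choose which scores qualify and whether single items count. That choice would then be made with data in hand.

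What is at stake is one part of a stated secondary objective. Protocol 6.10 presents the QLQ-BIL21 as the only questionnaire aimed specifically at patients with cholangiocarcinoma, so this is the instrument for which a disease-specific MID is most wanted. No primary endpoint, error rate or sample size is involved.

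**Working it through.** The plan states no figure to reproduce. The check is a count of scales, followed by a comparison of the sections.

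**Step 1. QLQ-BIL21 scores (SAP 3.2.7.2.5.3 and Table 7).** Items per scale for eating, jaundice, tiredness, pain, anxiety, side effects, drainage and weight loss: 4 + 3 + 3 + 4 + 4 + 1 + 1 + 1 = 21 items, in 5 + 3 = 8 scales/items. The five multi-item measures are described as symptoms, and none of the eight is labelled functional. Literal reach of the MID sentence: 0 of 8.

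**Step 2. QLQ-C30 scores (Table 6).** 1 global + 5 functional + 9 symptom scales/items = 15. Literal reach of the same sentence: 5 of 15, leaving out 1 + 9 = 10.

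**Step 3. Compare the sections.**

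| Place | What gets an MID | QLQ-BIL21 reach |
|---|---|---|
| SAP 1.2.2, protocol 2.2 | HRQoL and symptom response, instrument named | not restricted |
| SAP 3.2.7.2.5 | each assessment | not restricted |
| SAP 3.2.7.2.5.1, protocol 6.10 | QLQ-BIL21 scales, named | up to 8 of 8 |
| SAP 3.2.7.2.5.3 | functional scales | 0 of 8 |

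**Step 4. Is the restriction a choice or a carry-over?** The MID sentence is identical to the QLQ-C30 one. The scoring text beside it also gives a formula for global health status, which is a QLQ-C30 scale and is not listed in Table 7. SAP Section 4, which lists changes from the protocol's analysis, mentions no restriction of MIDs to functional scales. The evidence favours a carry-over.

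**Step 5. Does the parent section settle the matter?** Not fully. Its two methods work on a summary score, and the SAP defines no summary score for the QLQ-BIL21. If the term means the score of each scale, the question of which scales remains. The instrument sections answer it: the EQ-5D section, for example, names the VAS as its target.

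**Step 6. Size of the corrected output.** Each scale has 2 intervals (baseline to C3D1, C3D1 to C5D1), 2 directions and 2 methods. For all eight QLQ-BIL21 scales/items that is up to 8 × 2 × 2 × 2 = 64 estimates. For the five multi-item scales alone it is up to 5 × 2 × 2 × 2 = 40. As literally written it is 0.

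**The case against.** The strongest reply is that the plan does provide for QLQ-BIL21 MIDs. The parent section promises one for each assessment, and the anchor statements in both documents name the QLQ-BIL21 scales. A sensible analyst would see the carried-over phrase and read past it. This stands in part. A reader might infer that no QLQ-BIL21 MID is planned at all, or that the instrument contributes nothing to the secondary objective. The documents do not support either inference. The general text plans such MIDs, and 3.2.7.2.5.3 still summarises every scale at each visit with change and percent change from baseline. The secondary endpoint in SAP 1.3.2 is change in HRQoL and symptom response, and protocol 10.6.2 analyses it mainly descriptively. What the reply leaves open is which scores qualify, because the only sentence that selects them selects none.

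A reader might also infer that QLQ-BIL21 scores cannot be computed, because the text refers to an item range in Table 7 and the table as available shows none. That cannot be relied on: a column may have been lost when the PDF was read, and the four-point response implies a range of 4 − 1 = 3. The symptom formula is printed in the section, so scoring can be worked out. The surplus formulas are untidy but do not block the analysis.

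For the QLQ-C30, the restriction points to five real scales. It can be executed and could be intended, so it is a weaker point than the QLQ-BIL21 one.

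Finally, the MID work is exploratory in method and tests no hypothesis. That limits the weight of the point but does not remove the contradiction.

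**Conclusion.** The point holds as an internal contradiction. The instrument-specific instruction reaches 0 of 8 QLQ-BIL21 scales/items, while the objective, the general rule and the anchor statements reach the instrument without restriction. Followed as written, 3.2.7.2.5.3 would drop the disease-specific questionnaire from the MID part of a secondary objective; its descriptive part would stay intact. This is more than a clerical slip, because the general section does not say which scores to use.

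The conclusion rests on the SAP's own labels for the QLQ-BIL21 scales. That the sentence was carried over from the QLQ-C30 section is an inference from identical wording; the contradiction does not depend on it.

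The secondary point is that QLQ-C30 MIDs are limited to 5 of 15 scales, although the objective covers symptom response and the anchor statement names the QLQ-C30 scales without restriction. This needs reconciling, but it is not shown to be an error.

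**What to change.** In SAP 3.2.7.2.5.3:

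- Replace the reference to functional scales in the MID sentence with the five multi-item scales (eating, jaundice, tiredness, pain, anxiety) and the three single items (treatment side effects, drainage bag/tube difficulties, weight-loss concerns).
- State that all eight are scored with the symptom formula and an item range of 3.
- Delete the functional-scale and global-health-status formulas from that section.

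In SAP 3.2.7.2.5.2, either extend the MIDs to global health status and the nine symptom scales/items, or record that the restriction to the five functional scales is intended and give the reason.

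The cost is small: a wording change in the SAP and additional rows in the MID outputs, up to 64 estimates for the QLQ-BIL21. Extending the QLQ-C30 would add up to 10 × 2 × 2 × 2 = 80. No new data are needed, since the questionnaires and the anchor item are already scheduled at C3D1 and C5D1 and the baseline questionnaires at C1D1.

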#### 3.2.7.3 Exploratory Analyses

#### 3.2.7.3.1 Disease Control Rate (Substudy 1 and Substudy 2)

Disease control rate (DCR) is defined as the achievement of confirmed CR or PR or SD (or Non-CR/Non-PD for patients with non-measurable disease) using RECIST 1.1 as assessed by BICR. Point estimates and exact 2-sided 95% CIs (Clopper-Pearson) will be provided by the Safety/ITT Population.

DCR by investigator assessment will also be analyzed for the Safety/ITT Population.

#### 3.2.7.3.2 Investigator Assessed Best Overall Response (Substudy 1 and 2)

In the primary analysis, tumor response will be based upon measurements evaluation by the BICR. However, an initial assessment of tumor response will be made by investigators at site. As an exploratory measure, analyses of best overall response will be conducted considering investigator assessment only, these will be summarized by the Safety/ITT, mITT and PP population.

#### 3.2.7.3.3 Investigator Assessed PFS (Substudy 1 and 2)

PFS as assessed by the investigators will be analyzed similarly as detailed in Section 3.2.7.2.1 for the Safety/ITT and mITT Population.

#### 3.2.7.3.4 TTP (Substudy 1 and 2)

TTP will be calculated as follows:

- a. TTP (on derazantinib): TTP will be calculated from the first date of receiving study drug until first radiographic disease progression per BICR.
- b. TTP (on the first prior line of systemic therapy): TTP will be calculated from the date of first prior line of systemic therapy until date of radiographic disease progression reported for that regimen
- c. TTP (on the last prior line of systemic therapy): TTP will be calculated from the date of last prior line of systemic therapy until date of first radiographic disease progression reported for that regimen

Missing dates for the prior line of systemic therapy will be imputed as detailed in Section 3.1.4. The dates for the prior lines will be sorted by ascending dates to determine the first and last lines of systemic therapy.

Censoring of the TTP variables are summarized in Table 8, 9 and 10 below:

Situation	Date of progression or censoring	Outcome
No baseline tumor assessments	Date of first dose	Censored
No post-baseline tumor evaluation	Date of first dose	Censored
Radiological progression on or prior	Date of radiological assessment of measured	Progressed
to EOT	lesions prior to EOT	
No radiological progression	Date of last radiological assessment of measured	Censored
	lesions prior to EOT	
Treatment discontinuation for	Date of last radiological assessment of measured	Censored
reasons other than radiological	lesions prior to EOT	

#### Table 8: Censoring scheme for TTP (on derazantinib)

disease progression by BICR		
Death	Date of last radiological assessment of measured	Censored
	lesions prior to EOT	
Radiological progression after more than two missed tumor assessment or after end of treatment	Date of last radiological assessment of measured lesions prior to radiological progression, or EOT	Censored

#### Table 9: Censoring scheme for TTP (first line)

Situation	Date of progression or censoring	Outcome
No radiological progression reported	Date of last dose of treatment for the regimen	Censored
for first regimen		

#### Table 10: Censoring scheme for TTP (last line)

Situation	Date of progression or censoring	Outcome
No radiological progression reported	Date of last dose of treatment for the regimen	Censored
for last progression		

This will be analyzed using Kaplan-Meier methodology (Kaplan & Meier 1958). The median duration of TTP will be presented along with the standard error and 2-sided 95% CI. If they are calculable, the 25th and 75th percentiles and the 2-sided 95% CIs around the percentiles will be presented. Kaplan-Meier estimates at 3, 6, 9 and 12 months will also be presented. The Kaplan-Meier survival curves will also be presented.

TTP by line of prior systemic therapy will also be performed similarly.

TTP assessed on the first and the last prior line of systemic therapy (reported) and TTP on derazantinib will be presented by a Kaplan-Meier survival curve.

#### 3.2.8 Analyses of Safety Data

Safety analyses will be performed for the Safety/ITT population.

#### 3.2.8.1 Adverse Events

AEs will be coded using the MedDRA and assigned the grades (severities) based on NCI CTCAE, Version 4.03. For AEs not listed in the NCI CTCAE version 4.03, a similar grading system should be used as follows:

- Grade 1: Mild AE
- Grade 2: Moderate AE
- Grade 3: Severe AE
- Grade 4: Life-threatening or disabling AE
- Grade 5: Death

A treatment-emergent adverse event (TEAE) is defined as an AE with start date on or after the date of first dose and up to 30 days after last dose of study treatment (or until the start of a new anticancer therapy, whichever occurs earlier).

An overall TEAE incidence summary table will be produced and will include the number and percentage of patients with any TEAE, with any TEAE assessed by the Investigator as related to drug (related/not related), and with any serious TEAEs, drug-related serious TEAEs, TEAEs leading to permanent study drug discontinuation, drug-related TEAEs leading to permanent study drug discontinuation, TEAEs leading to study drug dose reduction or interruption, TEAEs leading to study drug dose reduction or interruption, drug-related TEAEs leading to study drug dose reduction or interruption, drug-related TEAEs leading to study drug dose reduction or interruption, drug-related TEAEs leading to study drug dose reduction or interruption, drug-related TEAEs leading to study drug dose reduction or interruption TEAEs leading to death, drug-related TEAEs leading to death will be summarized. The number of events will also be displayed.

For all event types listed above in the overall AE incidence summary table, tabulations by SOC and PT will also be produced. These will be presented by SOC and PT, sorted by decreasing frequency. Furthermore, TEAE, and drug-related TEAEs will also be summarized by SOC, PT, and maximum CTCAE grade, and sorted by decreasing frequency. Patients with more than one AE within a particular SOC are counted only once for that SOC. Similarly, patients with more than one AE within a particular PT are counted only once for that PT. For summaries by maximum CTCAE grade, patients with multiple AEs within a particular SOC or PT will be counted under the category of their most severe AE within that SOC or PT. AEs with missing CTCAE grade will be included in the missing counts.

The following TEAEs and drug-related TEAEs of special interest will also be presented by SOC and PT and sorted by decreasing frequency: Transaminase elevations, hyperphosphatemia, blood creatinine increased, nail toxicity, dry eye, corneal, and specific eye TEAEs (keratitis, retinal events, asthenia/fatigue, dry eye/xerophthalmia).

No formal hypothesis-testing analysis of AE incidence rates will be performed.

TEAEs will be listed in patient data listings. By-patient listings also will be provided for the following: patient deaths, serious adverse events (SAEs), and AEs leading to withdrawal.

